1.2. Rationale for the study

This study aims to estimate the burden of dengue illness in selected sites in South Asia and to prepare sites for the conduct of future vaccine efficacy trials.

Operational goals include:

- Build long-term collaboration with sites in dengue-endemic regions of South Asia where the incidence of clinical dengue illness can be studied.
- Establish dengue surveillance cohorts that can be followed long-term.
- Establish operational feasibility of future Phase III studies with regard to recruitment, case capture and sampling procedures.
- Prepare sites for participation in Phase III clinical endpoint studies

2. OBJECTIVES

2.1. Primary objective

- To determine the incidence of acute febrile illness (AFI) due to Laboratory Confirmed Dengue (LCD) in the study population.

Refer to Section 9.1.1 for the definition of the primary endpoint.

2.2. Secondary objectives

- To determine the incidence of AFI due to non-LCD in the study population.
- To describe the signs and symptoms of AFI due to LCD and of AFI due to non-LCD.
- To estimate the incidence of AFI due to LCD by Dengue Virus (DENV) type, study site, and age group.

Refer to Section 9.1.2 for the definition of the secondary endpoints.

2.3. Tertiary (research) objectives

(Amended 01 March 2017)

- To describe DENV and Japanese Encephalitis Virus (JEV) antibody profiles in subsets of subjects with AFI.
- To assess the concordance between dengue Reverse transcriptase-quantitative Polymerase Chain Reaction (RT-qPCR) and Non-Structural protein 1 (NS1)-antigen ImmunoChromatographic (ICT) test and/or Enzyme-Linked Immunosorbent Assay (ELISA) in the assessment of dengue infection.
- To gather clinical data that will support the definition of clinical endpoints for future efficacy trials.
- To describe spatio-temporal clustering of LCD cases.
- To describe entomological characteristics at selected site(s).
- To estimate the prevalence and incidence of tuberculosis diagnosis in the study population.
- To describe the incidence of hospitalisation and discharge diagnosis in the study population.
- To isolate and characterise infectious agents from a subset of subjects with AFI.
- To evaluate the antibody response to infectious agents in a subset of subjects with AFI.

Refer to Section 9.1.3 for the definition of the tertiary (research) endpoints.

[figure not shown]
3. STUDY DESIGN OVERVIEW

Protocol waivers or exemptions are not allowed. Therefore, adherence to the study design requirements, including those specified in the outline of study procedures (Section 6.4), are essential and required for study conduct.

Figure 1 Study design overview

[figure not shown]
Scheduled Visits

- Visit 1 and Visit 2 will take place **at home or** at the hospital/clinic
- Weekly contacts will be home visits (at least every other week) or **telephone contacts (TCs)**

Unscheduled Visits

- Suspected Dengue First Visit (hospital/clinic)
- Optional Return Visit (hospital/clinic)
- Suspected Dengue Follow-up Visit (hospital/clinic or home)

Notes: (Amended 01 March 2017)

The weekly contact may be a face to face visit outside the home in certain cases (i.e. at hospital during suspected dengue visit)

An unscheduled visit (either for first, return, or follow-up dengue visit) will be considered as the weekly contact for the week in which it occurs.

- **Type of design:** Prospective, community-based, cohort study, household-sampling, **single country.** (Amended 01 March 2017)
- **Study population:** Approximately **2000** subjects aged between 6 months and 50 years at the time of enrolment living in randomly selected households in geographically-defined communities. Households including at least one member aged less than 18 years will be considered eligible if at least one adult (aged no more than 50 years) and one child (aged less than 18 years) consent (and assent if applicable) to participate in the study. (Amended 01 March 2017)

- **Study visits:** The study will consist of scheduled visits (the enrolment visit [Visit 1], weekly contacts, and the close-out visit [Visit 2]) and, in case of AFI*, unscheduled Suspected Dengue Visits:
 - Visit 1 and Visit 2 will take place at home or at the hospital/clinic, in accordance with local ethics committee requirements and/or national laws or regulations
 - Weekly contacts will be home visits (at least every other week) or telephone contacts (TCs). *The weekly contact may be a face to face visit outside the home in certain cases (i.e. at hospital during suspected dengue visit)*
(Amended 01 March 2017)
 - Unscheduled Suspected Dengue Visits will take place in case of AFI*

*AFI is defined as fever (body temperature $\geq 38^{\circ}\text{C}/\geq 100.4^{\circ}\text{F}$) on ≥ 2 consecutive calendar days, measured at least twice, at least 8 hours apart.

- **Biological samples:** Blood samples will be collected at each Suspected Dengue First Visit.
- **Type of study:** self-contained.
- **Data collection:** Electronic Case Report Form (eCRF).
- **Duration of the study:** approximately 2 years per subject:
- **Epoch 001:** prospective data collection starting at Visit 1 (Month 0) and ending at Visit 2 (Month 24).

Table 1 Study groups and epochs foreseen in the study

Study Groups	Number of subjects	Age (Min/Max)	Epoch 001
Prospective	≈ 2000	6 months to 50 years	x

(Amended 01 March 2017)

3.1. Discussion of study design

This prospective cohort study including children aged less than 18 years and adults aged up to 50 years is designed to support the selection and definition of clinical and laboratory endpoints for future dengue vaccine efficacy trials and to provide incidence data for sample size calculation. In addition, the study aims to train investigators and their teams on protocol specific processes and procedures, in preparation for the conduct of anticipated future vaccine efficacy studies. **(Amended 01 March 2017)**

4. CASE DEFINITION

4.1. Acute febrile illness due to LCD

ALL of the following findings must be met for an AFI due to LCD (see [Figure 2](#)):

- Fever (body temperature $\geq 38^{\circ}\text{C}/\geq 100.4^{\circ}\text{F}$) on ≥ 2 consecutive calendar days, measured at least twice, at least 8 hours apart, and
- Laboratory confirmation of dengue through dengue RT-qPCR on the acute serum sample taken during the 7-day period (Days 2-7) from the onset of fever (body temperature $\geq 38^{\circ}\text{C}/\geq 100.4^{\circ}\text{F}$)

4.2. Acute febrile illness due to non-LCD

[figure not shown]
ALL of the following findings must be met for an AFI due to non-LCD (see [Figure 2](#)):

- Fever (body temperature $\geq 38^{\circ}\text{C}/\geq 100.4^{\circ}\text{F}$) on ≥ 2 consecutive calendar days, measured at least twice, at least 8 hours apart, and
- Dengue RT-qPCR result on the acute serum sample taken during the 7-day period (Days 2-7) from the onset of fever (body temperature $\geq 38^{\circ}\text{C}/\geq 100.4^{\circ}\text{F}$) is (valid but) negative for dengue

4.3. Undetermined cases

At least ONE of the following findings must be met for an undetermined case (see [Figure 2](#))

- Fever (body temperature $\geq 38^{\circ}\text{C}/\geq 100.4^{\circ}\text{F}$) on ≥ 2 consecutive calendar days, measured at least twice, at least 8 hours apart in a subject who has not been evaluated (at a Suspected Dengue First Visit or directly in a hospital/clinic) within the 7-day period (Days 2-7) from the onset of fever or who had an obvious alternative diagnosis other than dengue (i.e., an identified focus of fever), and therefore dengue RT-qPCR was not requested, or
- Dengue RT-qPCR result on the acute serum sample taken during the 7-day period (Days 2-7) from the onset of fever (body temperature $\geq 38^{\circ}\text{C}/\geq 100.4^{\circ}\text{F}$) is invalid or missing

Figure 2 Schematic overview of different cases

AFI: Acute febrile illness; **LCD:** Laboratory confirmed dengue; **RT-qPCR:** Reverse transcriptase quantitative polymerase chain reaction (Amended 01 March 2017)

Note: Two consecutive calendar days without fever (body temperature $\geq 38^{\circ}\text{C}/\geq 100.4^{\circ}\text{F}$), in the absence of antipyretic medication, are required to separate two episodes of fever.

Note: Subjects with fever (body temperature $\geq 38^{\circ}\text{C}/\geq 100.4^{\circ}\text{F}$) on ≥ 2 consecutive calendar days, measured at least twice, at least 8 hours who fail to attend a Suspected Dengue First Visit as they were directly hospitalised will be recorded as LCD, non-LCD or undetermined cases depending on the availability and result of the dengue RT-qPCR test. Refer to the Study Procedures Manual (SPM) for more information.

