6.5.4.3. Recording of serious adverse events related to study participation

Refer to Section 6.5.2.6.

6.5.5. Procedures at Suspected Dengue Visits**6.5.5.1. Procedures at Suspected Dengue First Visit*****6.5.5.1.1. Important general remarks***

All study subjects with AFI (fever [body temperature $\geq 38^{\circ}\text{C}/\geq 100.4^{\circ}\text{F}$] on ≥ 2 consecutive calendar days, measured at least twice, at least 8 hours apart) should be seen at a designated study hospital/clinic by the study physician. The Suspected Dengue First Visit should be scheduled within 7 days from the onset of fever (Days 2-7) and should ideally take place on the second day of fever (Day 2).

If a subject with fever (body temperature $\geq 38^{\circ}\text{C}/\geq 100.4^{\circ}\text{F}$) on ≥ 2 consecutive calendar days, measured at least twice, at least 8 hours apart has not been evaluated at a Suspected Dengue First Visit (or directly in a hospital/clinic) within the 7-day period (Days 2-7) from the onset of fever, the Suspected Dengue First Visit is no longer required and the case will be considered as an undetermined case. If a diary card has been filled, the data needs to be recorded in the eCRF.

Blood samples for study procedures should not be drawn from subjects who attend a study healthcare facility on the first day of fever (body temperature $\geq 38^{\circ}\text{C}/\geq 100.4^{\circ}\text{F}$), i.e., on Day 1. Medical assistance can be provided to these subjects but they will be asked to come back the following day should the fever persist. Blood samples for study procedures should only be drawn from the second day of fever (i.e., from Day 2, the second calendar day with fever) and onwards, up to Day 7.

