6.5.5.1.4. Blood sampling

Blood samples should only be drawn in case of AFI (i.e., fever [body temperature $\geq 38^{\circ}\text{C}/\geq 100.4^{\circ}\text{F}$] on ≥ 2 consecutive calendar days, measured at least twice, at least 8 hours apart) during the Suspected Dengue First Visit from the second day of fever (i.e., from Day 2, the second calendar day with fever) and onwards, up to Day 7.

The following blood samples should be collected unless an obvious alternative diagnosis, i.e., an obvious cause of fever other than dengue, has been identified and is documented (Amended 01 March 2017):

- Whole blood for laboratory confirmation of dengue by NS1-antigen (ICT test and/or ELISA): 0.5 mL, from all subjects (any age). The results of this/these test(s) should be recorded in the eCRF.
- Whole blood for laboratory confirmation of dengue infection by (generic and/or serotype-specific) RT-qPCR: 2.5 mL, from all subjects (any age).

- Whole blood for haematology assessment (complete blood count): 2 mL, from all subjects \geq 5 years of age and from subjects $<$ 5 years of age only if clinically indicated, as per investigator judgement or local recommendations. The results of these tests should be recorded in the eCRF.
- Whole blood for other tertiary (research) endpoints related tests (including, but not limited to, neutralising antibody against JEV and Chikungunya virus, tissue culture to isolate infectious agents, and sequencing to characterise infectious agents): **3.5 mL**, from all subjects \geq 18 years of age. A subset of these samples will be tested.

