5.3. Secondary objective

5.3.1. Analysis of secondary objective planned in the protocol

The incidence rate of first AFI due to LCD by serotype (DENV 1 – 4) and incidence rate of AFI due to non-LCD with 95% exact confidence interval will be calculated for overall and age group (could you please put here the age categories?).

Description of signs and symptoms of AFI due to LCD and due to non-LCD will include the percentage of AFI presenting each sign or symptom (any intensity and grade 3) during the 7-day period from the onset of fever (body temperature 38°C/100.4°F). The sign or symptom of suspected dengue infection is summarized in Table 1. Duration of signs and symptoms will also be described for LCD and non-LCD episodes. Analysis will be done overall and then separately by age group.

Table 1 Solicited symptoms of suspected dengue infection

Signs and symptoms
body temperature and route (minimum of two measurements)
headache / irritability
eye pain
myalgia (muscle pain)
arthralgia (joint pain)
abdominal pain
nausea
vomiting
rash
any bleeding (skin, mouth, anus)
loss of appetite
Fatigue/decrease in normal activity
reduced fluid intake

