DENV – 3 LCD	
[Fever (body temp \geq 38 C /100.4 F) on at least 2 consecutive days are measured at least twice, least twice 8 hours apart
 
AND
 
Dengue 3 specific RT-qPCR result during the 7-day period from fever is positive
	
[Fever (body temp \geq 38 C /100.4 F) on at least 2 consecutive days are measured at least twice, OR
 
Fever (body temp \geq 38 C /100.4 F) on at least 1 day is measured at least twice 8 hours apart
 
AND
 
Clinical suspicion of dengue base on solicited symptoms], AND
 
Dengue 3 specific RT-qPCR result during the 7-day period from fever is positive

DENV – 4 LCD	
[Fever (body temp \geq 38 C /100.4 F) on at least 2 consecutive days are measured at least twice, at least twice 8 hours apart
	
[Fever (body temp \geq 38 C /100.4 F) on at least 2 consecutive days are measured at least twice, OR

Endpoint	Case definition	Case definition for ad-hoc Analysis
	
AND
 
Dengue 4 specific RT-qPCR result during the 7-day period from fever is positive
	
Fever (body temp ≥ 38 C /100.4 F) on at least 1 day is measured at least twice 8 hours apart
 
AND
 
Clinical suspicion of dengue base on solicited symptoms], AND
 
Dengue 4 specific RT-qPCR result during the 7-day period from fever is positive

Non LCD	
[Fever (body temp ≥ 38 C /100.4 F) on at least 2 consecutive days are measured at least twice, at least twice 8 hours apart
 
AND
 
Dengue RT-qPCR result during the 7-day period from fever is negative
	
[Fever (body temp ≥ 38 C /100.4 F) on at least 2 consecutive days are measured at least twice, OR
 
Fever (body temp ≥ 38 C /100.4 F) on at least 1 day is measured at least twice 8 hours apart
 
AND
 
Clinical suspicion of dengue base on solicited symptoms], AND
 
Dengue RT-qPCR result during the 7-day period from fever is negative

Undetermined	
[Fever (body temp ≥ 38 C /100.4 F) on at least 2 consecutive days are measured at least twice, at least twice 8 hour apart
 
AND
 
Dengue RT-qPCR result during the 7-day period from fever is invalid or missing
	
[Fever (body temp ≥ 38 C /100.4 F) on at least 2 consecutive days are measured at least twice, OR
 
Fever (body temp ≥ 38 C /100.4 F) on at least 1 day is measured at least twice 8 hour apart

Endpoint	Case definition	Case definition for ad-hoc Analysis

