10.1.1.2. Laboratory data

Missing laboratory results (including immunological data) will not be replaced.

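### Fevers without a valid PCR are pooled as undetermined with no planned output in the SAP text, so the non-LCD rate understates non-dengue AFI and the LCD rate may be low

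*Protocol*

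**What the plan says.** - **Sampling.** Protocol 6.5.5.1.4 says that the study blood samples "should be collected unless an obvious alternative diagnosis, i.e., an obvious cause of fever other than dengue, has been identified and is documented".
- **Undetermined.** Protocol 4.3 puts into one class the AFI in a subject "who had an obvious alternative diagnosis other than dengue (i.e., an identified focus of fever), and therefore dengue RT-qPCR was not requested", the AFI not evaluated on Days 2-7, and the AFI with an invalid or missing PCR. Protocol 6.5.5.1.1 repeats the rule for late cases: "the Suspected Dengue First Visit is no longer required and the case will be considered as an undetermined case". SAP Table 2 (section 9.1.1) keeps only the laboratory condition, "Dengue RT-qPCR result during the 7-day period from fever is invalid or missing", so the reason is no longer visible.
- **Non-LCD.** Protocol 4.2 requires that the PCR result on a Day 2-7 sample "is (valid but) negative for dengue".
- **Planned rates.** SAP 5.2.1 plans the LCD rate. SAP 5.3.1 adds LCD by serotype and states that the "incidence rate of AFI due to non-LCD with 95% exact confidence interval will be calculated". Neither SAP 5.2 to 5.4 nor Protocol 9.6 and 9.7 mentions undetermined AFIs or a rate for all AFI.
- **Time at risk.** Protocol 9.4 and SAP 9.2.1 run it to the event of interest or the last contact, and the SAP adds death. SAP 10.1.2.3 ends it at the first AFI without naming a cause.
- **Missing results.** SAP 10.1.1.2: "Missing laboratory results (including immunological data) will not be replaced".

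**The concern.** A fever with an obvious non-dengue cause is not bled, so it cannot have the negative PCR that non-LCD requires. The fevers that are most clearly not dengue therefore fall outside the rate a reader would take as the burden of non-dengue fever. They also drop out of the comparator when LCD and non-LCD symptoms are set side by side (SAP 5.3.1 and 5.4.1).

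For the primary rate, the exposure lies in AFIs seen too late, never evaluated, or with a failed PCR. Late cases are foreseeable: Protocol Table 4 allows 6 to 8 days between weekly contacts, and sampling closes on Day 7.

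Protocol 3.1 says that the study is to supply incidence data for sizing a vaccine trial, and Protocol 1.2 names case capture and sampling as operational goals. The share of undetermined AFIs, by reason, measures case capture directly, yet the SAP text gives it no table.

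**Working it through.** **1. Follow each kind of AFI through the rules** (Protocol 9.4 and SAP 9.2.1 for time at risk)

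| AFI | Class | LCD event | Non-LCD event | Time at risk |
|---|---|---|---|---|
| PCR positive | LCD | yes | no | ends for LCD |
| PCR valid and negative | non-LCD | no | yes | ends for non-LCD |
| (a) alternative diagnosis, PCR not requested | undetermined | no | no | continues for both |
| (b) not evaluated on Days 2-7 | undetermined | no | no | continues for both |
| (c) PCR invalid or missing | undetermined | no | no | continues for both |

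As measures of dengue and non-dengue febrile illness, the two rates can therefore only be too low or unchanged.

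**2. Reproduce the plan's figures** (Protocol 9.2)

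- Person-years: 2000 × 0.9 + 2000 × 0.9 × 0.8 = 3240, against about 3300 stated.
- Table 17 at 40 cases: 40/3300 = 1.21 per 100 person-years; exact limits 0.87 to 1.65. With design effect 2.6, the half-width is 1.96 × √(2.6 × 40)/3300 = 0.61 per 100, giving 0.61 to 1.82. Both match, as do the other nine rows.

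**3. LCD rate**

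Neither input is in the documents; both are assumed.

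- u: share of AFIs outside class (a) that fall in (b) or (c).
- r: PCR positivity in those AFIs relative to tested ones, from 0 to 1.

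Per AFI outside (a), with positivity q among the tested, observed cases are q(1 − u) and missed cases are rqu. With person-years held fixed, true/planned = 1 + r·u/(1 − u). Applied to 40 cases in 3300 person-years (multiplier, then rate per 100 person-years):

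| u | r = 0 | r = 0.5 | r = 1 |
|---|---|---|---|
| 5% | 1.00; 1.21 | 1.03; 1.24 | 1.05; 1.28 |
| 10% | 1.00; 1.21 | 1.06; 1.28 | 1.11; 1.35 |
| 20% | 1.00; 1.21 | 1.13; 1.36 | 1.25; 1.52 |
| 30% | 1.00; 1.21 | 1.21; 1.47 | 1.43; 1.73 |

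Only the last cell exceeds the exact upper limit of 1.65, and it stays below the design-effect limit of 1.82.

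**4. Non-LCD rate**

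Let w be the share of all AFIs that are undetermined for any reason, q the PCR-positive share among tested AFIs (assumed 5 to 20%), and r the positivity of undetermined AFIs relative to tested ones (0 to 1). Per episode, the share of non-dengue AFI captured is (1 − w)(1 − q)/[(1 − w)(1 − q) + w(1 − qr)]. For w = 20% and q = 20%, it is 0.64/(0.64 + 0.20) = 76% at r = 0 and 0.64/(0.64 + 0.16) = 80% at r = 1.

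| w | captured | shortfall |
|---|---|---|
| 10% | 88-90% | 10-12% |
| 20% | 76-80% | 20-24% |
| 30% | 65-70% | 30-35% |
| 40% | 55-60% | 40-45% |

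These figures are per episode. SAP 9.2.1 counts subjects with at least one episode, so a subject with one untested and one tested-negative AFI still counts. For illustration, assume 0.2 non-dengue AFIs per subject-year over two years, constant and equal risk, and 30% untested at random. The share of subjects with a countable AFI falls from 1 − e^(−0.4) = 0.330 to 1 − e^(−0.28) = 0.244, a loss of 26% and not 30%. Letting time at risk run on to the later episode moves the loss in the rate back towards 30%. The per-episode figures are best read as the outer end.

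**5. The conflicting time-at-risk rule**

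Read literally, SAP 10.1.2.3 stops the clock at any AFI. At assumed AFI rates of 0.1 or 0.3 per person-year and two years without drop-out, it would keep (1 − e^(−2λ))/(2λ) = 91% or 75% of person-years. The denominator is not settled until the sections agree.

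**The case against.** The strongest reply is that non-LCD is defined in advance as AFI with a valid negative PCR, that the three classes are deliberate, and that the planned rate estimates exactly that quantity. This stands. A reader might infer that the non-LCD analysis is wrong for its own endpoint; it is not. The rate falls short only as a measure of all non-dengue AFI, and the plan gives the reader nothing with which to see the difference.

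Other points also stand in part:

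- A reader might take 25% as a known bias in the primary rate. It is the equal-positivity end of an assumed range; at r = 0 there is none.
- A reader might think that the alternative-diagnosis AFIs depress the LCD rate. They do so little if dengue is rare among them.
- The rule on missing laboratory results is a generic one in the annex. It does not show that missing PCRs are treated as negative; those AFIs have their own class. The non-event status follows from the numerator and time-at-risk rules.
- It would go too far to say that no output will show the loss. SAP 10.2 places the table shells elsewhere, and Table 2 lists undetermined in its endpoint column, so a count may exist there.
- The planned NS1 incidence (Protocol 9.7, SAP 5.4.1) can pick up dengue where blood was taken but the PCR failed. It cannot help where no blood was drawn.
- All analyses are descriptive (SAP 6), so no test decision is at risk.

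**Conclusion.** The concern holds as a gap in reporting and sensitivity analysis. The SAP text plans no count, rate or sensitivity analysis for undetermined AFIs, and under Protocol 9.4 and SAP 9.2.1 they contribute person-time and no event. The non-LCD rate understates non-dengue AFI, mainly through class (a), by an amount usually somewhat below the untested share of episodes. The LCD rate may be understated, mainly through (b) and (c), by a factor of 1 + r·u/(1 − u); at u = 20% that is 1.00 to 1.25.

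The direction rests on the documents. The size does not: u, r, q and w are all assumptions, and the arithmetic for both rates holds person-years fixed. The conclusion about person-time also depends on SAP 9.2.1 prevailing over SAP 10.1.2.3.

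**What to change.** Keep the planned LCD and non-LCD rates as primary, and change no case definition or sampling procedure.

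1. **SAP Table 2:** split undetermined into (a) alternative diagnosis, PCR not requested; (b) not evaluated on Days 2-7; (c) PCR invalid or missing. Use the recorded reason where available.
2. **SAP 5.3.1:** report counts and incidence of (a), (b), (c) and all AFI, overall and by age group. Report non-LCD incidence as planned and as non-LCD plus (a).
3. **SAP 5.2:** add a labelled LCD sensitivity rate that gives (b) and (c) a positivity of r times that of tested AFIs, for r from 0 to 1. Use NS1 results where the PCR is invalid or missing but NS1 was done. Do this overall or by broad age band only: four age bands by eight calendar quarters would make 32 cells, about 40/32 = 1.25 cases each at 40 cases.
4. **SAP 10.1.2.3:** reconcile with SAP 9.2.1 and Protocol 9.4 so that time at risk ends at the event of interest and not at any AFI.

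The cost is SAP wording and a few tables. The sensitivity rate rests on a positivity assumption that cannot be tested. Protocol 6.5.5.1.4 requires the alternative diagnosis to be documented but names the eCRF only for NS1 and haematology results. The reason may therefore not be an analysable field, and enrolment was complete when the SAP was written. Where the reason cannot be recovered, show it as unknown.
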